### 9.4.2 ANALYSIS OF THE PRIMARY ENDPOINT(S)

The following key outcomes will be assessed in this study. All measures are interval with the exception of the categorical covariate of sex.

- Subjective effort
  - Likert scale ratings (ranging from 1-10) of task-induced effort, demand, time pressure, and stress
  - subjective values as estimated from an indifference point discounting procedure
  - self-reported motivation to engage in demanding tasks on a set of Likert scales with continuous values ranging from 0-20
  - Pupil dilation as a continuous variable which has been shown to index the cognitive and physical effort associated with oculomotor tasks (Koevoet et al., 2024)
- E/I balance
  - fEI derived measure with exponents ranging approximately from 0.0-2.0
  - avalanche branching statistics with values approximately from 0.5 to 1.5
  - power-law exponents with exponents approximating -2.0
- Critical dynamics
  - Long range temporal correlations – a derived measure with exponents ranging approximately from 0.5-1.0
  - Avalanche size and duration distribution exponents approximating -2.0 and -1.5, respectively.

- Band-limited bistability with values ranging from 0.0 to ~5.0
- Memory guided saccade task performance
  - overall accuracy as degrees of visual angle
  - median reaction times in terms of time from cue until a saccade is launched
  - trial-wise variability in accuracy (SD)
  - trial-wise variability in reaction time (SD)
- Anti-saccade task performance
  - Overall accuracy rate as a percent of trials with correct anti-saccade versus incorrect pro-saccade
  - Median reaction times in terms of time from cue until a saccade is launched
  - trial-wise variability in accuracy (SD)
  - trial-wise variability in reaction time (SD)

Primary analyses of these outcomes will entail multiple regression models in which outcomes will be regressed on cTBS condition (target versus sham), controlling for sex and age.

We will also test for inter-correlations among the primary endpoint measures. Namely, these correlations will test whether the degree to which rTMS alters one measure (e.g. functional E/I balance) correlates with stimulation effects on other measures (e.g. endpoint variability on the memory-guided saccade task).

We will use Pearson's correlations for all tests since our outcome measures are continuous, interval measures.

---

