## 6 STUDY INTERVENTION(S) OR EXPERIMENTAL MANIPULATION(S)

### 6.1 STUDY INTERVENTION(S) OR EXPERIMENTAL MANIPULATION(S) ADMINISTRATION

#### 6.1.1 STUDY INTERVENTION OR EXPERIMENTAL MANIPULATION DESCRIPTION

The study intervention is modulation of cortical excitation to inhibition (E/I) balance in the right frontal eye field (FEF) by means of 2 trains of spaced continuous theta burst stimulation (cTBS) or intermittent theta burst stimulation (iTBS) using a transcranial magnetic stimulation device. As prior work (Huang et al 2005; Chung et al. 2018) has shown that cTBS reliably decreases the cortical E/I ratio with diverse cortical targets and iTBS increases the E/I ratio, we expect to replicate a reduction in E/I balance when cTBS is applied to the FEF and an increase in E/I balance when iTBS is applied. The mechanism of action is thought to be a manipulation of inhibitory neurotransmission across diverse timescales. The endpoint of this stimulation will be a modulation of the local E/I ratio that should last at least 60 minutes post-stimulation (Chung et al., 2016).

We will assess the changes in E/I balance by quantifying the functional E/I ratio as previously done in a study of the GABA receptor agonist Zolpidem (Bruining et al. 2020). We furthermore anticipate that a reduction in FEF E/I balance will also make the dynamics of FEF more sub-critical while an increase would make FEF more super-critical (Pfeffer et al. 2018; Poil et al. 2012). Thus, depending on whether participants' brains operate in a sub- or super-critical regime at baseline, we predict that cTBS and iTBS manipulations will either make their brains operate closer to or farther from criticality. If cTBS / iTBS make participants' brains operate closer to criticality, this will be reflected by an inferred functional E/I ratio of 1.0, and stronger long range temporal correlations. Conversely values farther from 1.0 will correspond with weaker long-range temporal correlations otherwise found in the brain in a critical state. Moreover, we will test the prediction that cTBS / iTBS to the FEF will affect oculomotor control. Specifically, we predict that since criticality affords maximal susceptibility and flexibility, tasks which require more stability (e.g. short term memory tasks) will be performed with less precision and more trial-to-trial variability in accuracy and reaction times at criticality. Since criticality also maximizes information transfer capacity,

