## 9.4 STATISTICAL ANALYSES

### 9.4.1 GENERAL APPROACH

There are no categorical outcomes. Key measures are all continuous outcomes, and are described in detail in the next section. They will be analyzed according to pre- versus post-stimulation means and also in sham versus active stimulation. We will also report standard errors for each outcome. Key outcomes have multiple associated measures. Multiple measures will be used to assess reliability by parallel forms.

We will use standard frequentist cut-offs of  $p < 0.05$  for all statistical tests, correcting for multiple comparisons. Key t-tests will include pre-post and sham-versus-active distinctions in E/I balance measures, oculomotor control task performance measures, and measures of criticality.

Covariates of no interest to be included are sex and age which we will incorporate via multiple regression to ask whether rTMS alters key outcomes (described in the next session).

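### As Section 9.4.2 defines accuracy, the anti-saccade accuracy SD is fixed by the accuracy rate and cannot test consistency separately; the avalanche reference exponents there also look transposed.

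*Protocol*

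**What the plan says.** Protocol Section 9.4.2 lists four measures for each saccade task.

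- **Memory-guided task.** Accuracy is continuous: "overall accuracy as degrees of visual angle". Its trial-to-trial SD is a separate item.
- **Anti-saccade task.** Accuracy is "Overall accuracy rate as a percent of trials with correct anti-saccade versus incorrect pro-saccade". The SD item is then repeated in the same words: "trial-wise variability in accuracy (SD"). A reaction-time SD is also listed.

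Section 9.4.1 states "There are no categorical outcomes. Key measures are all continuous outcomes" and sets p < 0.05 "for all statistical tests, correcting for multiple comparisons". Section 9.4.2 adds Pearson correlations among the endpoints: "these correlations will test whether the degree to which rTMS alters one measure" in step with its effect on others. Section 6.1.1 predicts that stimulation which moves the frontal eye field closer to criticality will make anti-saccade performance both better and less variable.

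Under critical dynamics, Section 9.4.2 also gives reference values: "Avalanche size and duration distribution exponents approximating -2.0 and -1.5, respectively". The protocol defines neither avalanche size nor avalanche duration. Section 3 puts the critical point at a branching ratio of 1.0.

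**The concern.** A correct/incorrect score has no spread of its own. Once the proportion correct is known, so is the SD. The anti-saccade SD looks like a measure of consistency but restates the rate on another scale. If accuracy rises from any level above 50%, the SD must fall, and the result would read as confirming the consistency prediction when only the accuracy prediction had been tested. A correlation between the stimulation effects on the two measures would likewise be partly arithmetic. Section 9 of the protocol says that no formal SAP is planned, so the protocol names no later document in which the item would be redefined.

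The exponents are a smaller matter. If they are transposed, anyone who takes them as the critical reference would compare each fitted exponent with the wrong value.

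**Working it through.** **1. The anti-saccade SD**

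Input from the protocol: each trial is either a correct anti-saccade or an incorrect pro-saccade (Section 9.4.2). Assumed, because the protocol does not give them: trial counts and accuracy levels.

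With n trials scored 0/1 and proportion p correct, the squared deviations from the mean sum to n·p(1-p). Hence

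SD = sqrt( n/(n-1) × p(1-p) ).

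For n = 100:

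| p | p(1-p) | SD |
|---|---|---|
| 0.70 | 0.2100 | 0.461 |
| 0.80 | 0.1600 | 0.402 |
| 0.90 | 0.0900 | 0.302 |
| 0.95 | 0.0475 | 0.219 |

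Since p(1-p) = 0.25 - (p - 0.5)², the SD falls as p rises above 0.5 and rises as p rises towards 0.5 from below. This holds for equal trial counts. Unequal counts change only the factor sqrt(n/(n-1)), which is 1.010 at n = 50 and 1.003 at n = 200.

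**2. The built-in correlation**

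Two sessions were simulated for 60 people with 50, 100 or 200 trials each. The mean shift in accuracy was 0 or 0.03, and the between-person SD of the shift was 0 or 0.05. The table gives the mean Pearson correlation between the change in rate and the change in SD.

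| Accuracies within | Correlation |
|---|---|
| 0.60 to 0.95 (including the narrower bands 0.70-0.95 and 0.60-0.85) | -0.75 to -0.92 |
| 0.50 to 0.95 | -0.65 to -0.77 |
| 0.40 to 0.80 | -0.57 to -0.63 |
| 0.30 to 0.90 | -0.37 to -0.47 |

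The link weakens when the sample straddles 50%, because the SD then rises with accuracy for some people and falls for others.

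**3. Effect on multiplicity**

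The list has 4 + 3 + 3 + 4 + 4 = 18 items. The protocol does not name its correction. If it were Bonferroni over items, the threshold would be 0.05/18 = 0.00278 with this item and 0.05/17 = 0.00294 without it.

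**4. The avalanche exponents**

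Input from the protocol: branching ratio 1.0 (Section 3). Assumed: size counts events and duration counts occupied time bins.

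- *Size, Poisson offspring:* P(S = n) = e^(-n) n^(n-1)/n!. The log-log slope from 1,000 to 10,000 is -1.500.
- *Duration:* q(0) = 0, q(t+1) = exp(q(t) - 1), P(T = t) = q(t) - q(t-1). The slope over the same range is -1.997.
- *Other offspring laws:* geometric gives -1.500 and -2.000; binomial(2) gives -1.500 and -1.993.

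The stated order, size -2.0 and duration -1.5, is not reproduced.

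An ordering check needs no branching model. Under the same counting, every occupied bin holds at least one event, so S ≥ T and P(S ≥ 100) ≥ P(T ≥ 100). Taking the stated values as discrete power laws from 1:

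- P(S ≥ 100) = zeta(2, 100)/zeta(2) = 0.0061
- P(T ≥ 100) = zeta(1.5, 100)/zeta(1.5) = 0.0768

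The inequality is violated.

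**The case against.** **The SD may refer to landing error.** The SD bullet repeats the memory-guided one, where accuracy is in degrees, and Section 9.4.1 says that no outcome is categorical. The authors may have had a continuous error in mind. That is possible, but nothing under the anti-saccade task says so, and the only accuracy defined there is correct versus incorrect. On either reading the text needs changing.

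**The group tests are not duplicates.** A reader might infer that testing the SD merely repeats the test of the rate. The simulations do not support that. Given a significant rate difference, the chance that the SD difference was also significant ran from 0.12 to 0.997 across the settings. What is fixed is each session's SD given its rate and trial count.

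**Overlap is intended, and the stakes are small.** Section 9.4.1 uses several measures per outcome to gauge reliability by parallel forms. Section 3 names accuracy, not variability, as the anti-saccade endpoint. The example correlation in Section 9.4.2 crosses domains. These points stand and limit the harm. Even so, a quantity computed from the rate is not a parallel form of it, and the multiplicity cost is too slight to carry any weight.

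**The exponents are descriptive.** They enter no stated test, sample size or decision rule. The order also depends on definitions that the protocol does not give: if size meant distinct active channels, the 64-channel system (Section 8.1) would cap it and the ordering argument would fail. Short fitting windows also move the estimate. For exactly critical processes fitted over 5 to 64 events, the expected size exponent was -1.494, -1.531 and -1.421 (Poisson, geometric, binomial). All of this stands, and so the exponents are only a side correction.

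**Reversed conclusions about criticality.** A reader might infer that the transposition would turn conclusions about criticality round. The protocol does not support this. Section 6.1.1 judges closeness to criticality by other measures: "this will be reflected by an inferred functional E/I ratio of 1.0, and stronger long range temporal correlations". Contrasts of fitted exponents, active versus sham or before versus after, do not use the reference values.

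**Conclusion.** The anti-saccade accuracy SD is wrong as written. On the definition in Section 9.4.2 it is an exact function of the accuracy rate and the trial count within each session. It cannot test the consistency prediction apart from the accuracy prediction, and above 50% accuracy a gain in rate is bound to look like a gain in consistency. This rests only on trials being scored 0/1, as the section states. The strength of the artefactual correlation is not settled by the protocol; the simulated range depends on assumed accuracies, trial counts and shifts.

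The exponents are very probably transposed, on condition that size counts events and duration counts occupied bins. That touches reference values only. It would matter only if they were later used to measure distance from criticality, and the reading would then reverse only where the midpoint of the two compared exponents lies between -2.0 and -1.5.

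Both matters are minor. Neither affects the sample size or any planned contrast on the other outcomes.

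**What to change.** In Section 9.4.2:

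1. Under the anti-saccade task, delete the accuracy SD. If a continuous error was meant, redefine the item as the trial-to-trial SD of landing error in degrees.
2. State that anti-saccade consistency will be tested with the reaction-time SD already listed.
3. Keep the accuracy SD for the memory-guided task, where accuracy is in degrees and the SD carries separate information.
4. State how avalanche size and duration are counted. If they count events and occupied time bins, restate the exponents as size about -1.5 and duration about -2.0, as reference values and not exact targets.

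The cost is wording, plus at most one fewer listed outcome. Data collection does not change if the SD is deleted; the landing-error option needs saccade endpoints to be scored in degrees for this task, as the memory-guided task already requires.

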### 3 OBJECTIVES AND ENDPOINTS

OBJECTIVES	ENDPOINTS	JUSTIFICATION FOR ENDPOINTS	PUTATIVE MECHANISMS OF ACTION
Primary			
Test whether theta-burst stimulation induces a shift towards super- (intermittent theta-burst stimulation, or iTBS) or sub-critical dynamics (continuous theta burst stimulation, or cTBS) in the cortex during rest.	Diminished markers of critical dynamics including reduced long-range temporal correlations measured by detrended fluctuation analysis, and super-critical and sub-critical avalanche branching ratios.	Long-range temporal correlations ( $< 1.0$ ) and avalanche branching dynamics are widely used metrics of distance from the critical point (degree of sub-: $< 1.0$ and super-criticality $> 1.0$ ) in EEG studies.	Long-range temporal correlations and avalanche branching ratios of 1.0 are emergent properties of dynamical systems at a critical point. By reducing and increasing the E/I balance, theta burst stimulation should make the brain more sub-critical and super-critical, respectively, thus dampening these

OBJECTIVES	ENDPOINTS	JUSTIFICATION FOR ENDPOINTS	PUTATIVE MECHANISMS OF ACTION
			emergent properties.
Test whether theta-burst stimulation to the frontal eye fields (FEF) alters cognitive control relative to sham stimulation.	Increases or decreases in accuracy in the anti-saccade task	Criticality affords the capacity for inter-regional communication in the service of, e.g., top-down control from FEF to saccade motor regions. Thus, people with brains operating closer to criticality should show greater accuracy on the anti-saccade task. If cTBS makes brains more sub-critical, they should show less anti-saccade accuracy. If iTBS makes brains more critical (or even super-critical) during tasks, then it should increase anti-saccade accuracy relative to sham stimulation.	A decrease in the E/I balance in the FEF following cTBS or an increase in E/I balance following iTBS should make brains more sub-critical or more super-critical, respectively, thus decreasing and increasing the capacity for top-down anti-saccade inhibition, respectively.

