### 9.1 STATISTICAL HYPOTHESES

- Primary Endpoint(s):

We predict that, relative to pre-stimulation rest, continuous theta burst stimulation (cTBS) will result in a reduction of the local balance of cortical excitation to inhibition as reflected in the functional E/I balance in proximity to stimulated targets. Conversely, we predict that intermittent theta burst stimulation (iTBS) will result in an increase of the local balance of cortical excitation to inhibition as reflected in the functional E/I balance in proximity to stimulated targets. We also predict these changes to exceed any effects of sham stimulation, and thus another set of endpoints will compare the functional E/I balance after sham versus either active stimulation protocol.

We also predict that, relative to pre-stimulation rest, cTBS and iTBS protocols that will either reduce or strengthen markers of critical dynamics (including, e.g., long-range temporal correlations) in proximity to stimulation targets. The direction of the effect will depend on how the brain operates at baseline. For example a brain that operates in a more sub-critical (lower E/I balance) regime will show an increase in long-range temporal correlations following iTBS (because it should raise the functional E/I balance).

We also predict that, relative to sham stimulation, cTBS and iTBS will alter oculomotor task performance. Specifically, because criticality makes brains more flexible and susceptible, protocols which make brains operate closer to criticality will cause performance to become more variable and worse on the memory-guided saccade task which depends on stability of short-term memory representations. Also, because criticality increases information transfer capacity between brain regions, protocols which make brains operate closer to criticality will cause performance to become better on the anti-saccade task which depends on robust top-down communication of control signals to override bottom-up reflexive saccades to the target.

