We also predict that, relative to sham stimulation, cTBS and iTBS will alter subjective effort. We hypothesize that subjective effort reflects divergence from criticality associated with performing difficult tasks. Indeed, typically, brains become more sub-critical, on average, when performing demanding tasks. To measure subjective effort, we will examine cognitive effort discounting – a measure of the amount by which participants discount the offer to perform a more demanding version of tasks (in this case with frequent task switching between anti- and pro-saccades) versus a less demanding version of the task (in this case with minimal task switching between anti- and pro-saccades) for money. The amount of money people forgo to avoid the harder task quantifies the subjective effort cost they experience. We predict

that people whose brains diverge more from criticality during task performance will show steeper effort discounting, and that cTBS or iTBS protocols that minimize divergence from criticality during the task will show shallower effort discounting.

We also hypothesize that subjective effort reflects divergence from a critical state and that criticality depends on the E/I balance. As such, we predict that there will be individual difference correlations in the degree to which TMS perturbs E/I balance, alters measures of criticality including long-range temporal correlations, and ultimately amplifies subjective effort.

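### Correlations in section 9.4.2 that start from E/I or branching ratio assume a straight line, while the protocol predicts a peak at 1.0, so they can miss a true effect

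*Protocol*

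**What the plan says.** **The test.** Section 9.4.2 will ask whether "the degree to which rTMS alters one measure (e.g. functional E/I balance) correlates with stimulation effects on other measures", and gives variability on the memory-guided saccade task as an example of the other measure. It prescribes Pearson's "correlations for all tests since our outcome measures are continuous, interval measures". Section 9.1 states the matching hypothesis as "individual difference correlations in the degree to which TMS perturbs E/I balance", in changes in criticality measures and in subjective effort. The only other model in 9.4.2 is one in which "outcomes will be regressed on cTBS condition (target versus sham), controlling for sex and age". It has no term for fEI, for baseline or for distance from 1.0. Section 9 adds that there will be no formal SAP, so this wording is the plan.

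**The theory.** Section 6.1.1 says that if stimulation brings a brain closer to criticality, "this will be reflected by an inferred functional E/I ratio of 1.0, and stronger long range temporal correlations". It continues: "Conversely values farther from 1.0 will correspond with weaker long-range temporal correlations". Section 3 treats super-critical and sub-critical shifts alike as "Diminished markers of critical dynamics including reduced long-range temporal correlations measured by detrended fluctuation analysis", and takes 1.0 as the critical branching ratio, with departures possible in either direction. Section 9.1 says of the criticality markers: "The direction of the effect will depend on how the brain operates at baseline". Section 9.4.2 gives fEI a range of about 0.0 to 2.0, so both sides of the peak can be observed.

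**The concern.** Pearson's r measures how well a straight line describes two variables. That the measures are continuous and interval, the only reason 9.4.2 gives, does not make their relation linear. If long-range temporal correlations (LRTC) peak at fEI 1.0, a rise in fEI strengthens them below 1.0 and weakens them above it. Participants on the two sides then pull the correlation in opposite directions.

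The correlations are the only analyses in 9.4.2 that connect E/I to criticality, performance and effort. A near-zero result could be read as evidence against the mechanism when it comes from the scoring of E/I change. If the scoring is settled after the data are seen, the test loses its confirmatory value.

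**Working it through.** **1. The plan's own figure.** Section 9.2 states 36% power for late iTBS (effect size 0.21 in magnitude, n = 60). A paired t-test, two-sided at 0.05, has noncentrality 0.21 x sqrt(60) = 1.63 and power 36.0%, so the figure reproduces. It concerns a mean shift. The protocol states no power for the correlations.

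**2. Algebra.** Take a quadratic peak: LRTC = -(x - 1)^2 with x = fEI, shared baseline b, and change d symmetric about its mean m. The change in LRTC is

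-(b + d - 1)^2 + (b - 1)^2 = -2(b - 1)d - d^2.

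Since Cov(d, d^2) = 2m Var(d) for symmetric d,

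Cov(d, change in LRTC) = -2 Var(d)(b + m - 1).

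This is zero whenever b + m = 1, that is, when mean post-stimulation fEI is 1.0, whatever the variance. Examples are iTBS with b = 0.9 and m = +0.1, cTBS with b = 1.1 and m = -0.1, and equal cTBS and iTBS shifts pooled with b = 1.0, where m = 0. Away from that point the covariance is not zero.

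**3. Simulation.** From the protocol: n = 60, alpha 0.05, peak at 1.0. Assumed, because the protocol gives no variances: fEI shift of mean -0.10 (cTBS) or +0.10 (iTBS) with SD 0.10; marker change = minus the change in distance from 1.0, plus noise of SD 0.07; fEI measured without error. There were 4,000 replicates, with two-sided tests. Entries are mean r and percentage significant.

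| Baseline fEI | Protocol | Raw change | Change in distance |
|---|---|---|---|
| 0.9, SD 0.1 | iTBS | 0.00 (11%) | -0.83 (100%) |
| 1.1, SD 0.1 | cTBS | 0.00 (11%) | -0.83 (100%) |
| 1.0, SD 0.2 | each alone | +0.25 cTBS, -0.25 iTBS (about 50%) | -0.86 (100%) |
| all at 1.0 | pooled | 0.00 (11%) | -0.75 (100%) |
| all at 1.0 | each alone | +0.64 cTBS, -0.64 iTBS (100%) | -0.75 (100%) |
| 0.9, SD 0.1 | cTBS | 0.70 (100%) | -0.81 (100%) |
| 0.8, SD 0.1 | iTBS | 0.45 (89%) | about -0.8 (100%) |
| 0.7, SD 0.1 | iTBS | 0.71 (100%) | -0.80 (100%) |

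The first four rows show where raw change fails or weakens. The last four show where it works.

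**4. Reading degree as size of change.** Section 9.4.2 does not say whether change keeps its sign. With absolute change, the all-at-1.0 case recovers (r = -0.75). iTBS from 0.9 (SD 0.1) stays weak at about -0.13, and iTBS from 0.7 (SD 0.1) reverses sign to +0.58.

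**5. Measurement error in fEI.** With error SD 0.10 on each reading, iTBS from 0.9 (SD 0.1) still gives raw r = 0.00 (6 to 7% significant) against about -0.46 for distance (96 to 98%). With all baselines at 1.0, the advantage disappears within a protocol: iTBS gives -0.37 and -0.38, each significant about 85% of the time. At error SD 0.15 raw change does better, about 55% against 45%.

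**6. Bias of the absolute distance.** For error SD s and true offset u = |x - 1|, the upward bias is s sqrt(2/pi) exp(-u^2/(2s^2)) + u[1 - 2 Phi(-u/s)] - u. With s = 0.10 it is 0.080 at fEI 1.0, 0.017 at 0.9 and 0.002 at 0.8. A participant moved from 0.9 to 1.0 has a true change in distance of -0.100 and an expected observed change of -0.100 + (0.080 - 0.017) = -0.037. A sham session that stays at 0.9 has expected change 0, so subtracting sham does not remove the bias.

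**The case against.** **The failure is confined to certain baselines.** This stands. Within a protocol it needs mean post-stimulation fEI near 1.0. Sections 2.2 and 9.1 say demanding tasks make brains more sub-critical, and values that stay below 1.0 suit raw change. But the protocol does not know where its participants lie, and stimulation that brings them to criticality on average is exactly where the test goes blind.

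**The pooled null needs pooling that is not stated.** This also stands. Section 9.4.2 speaks of rTMS without separating the protocols, but never says that cTBS and iTBS changes enter one correlation, and 9.1 makes separate predictions. Section 2.1 places the resting brain near a critical point; it does not put every participant at 1.0. Opposite signs in the two protocols at that baseline are what a peak predicts, and would not count against the theory.

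**The wording may mean size of change.** Possible, but step 4 shows that this rescues only the all-at-1.0 case.

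**The simulation favours the remedy.** Data generated from distance are tested with distance, so -0.83 and 100% is a best case. Step 5 shows the advantage surviving fEI error at baseline 0.9 and vanishing when everyone sits at 1.0.

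**The anti-saccade row of section 3 predicts one direction per protocol.** It does, and that fits a straight line. It sits uneasily with the peak and the baseline dependence in 6.1.1 and 9.1, and does not remove them.

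**Conclusion.** The point holds within limits. For correlations that start from fEI or branching ratio, 9.4.2 fixes a linear form that the protocol's own theory does not support, and the result can be near zero when the theory is true. Under the assumed variances the loss is complete for iTBS from a baseline near 0.9 (11% significant against 100%), partial for mixed baselines around 1.0 (about 50% against 100%), and absent or small when participants stay on one side of 1.0. The algebraic zero does not depend on the variances; the simulated sizes do.

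A reader might infer more than the documents support:

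- That these correlations will be null. They can be, for some baselines.
- That the whole chain is mis-tested. Sections 6.1.1 and 9.1 predict monotone links from closeness to criticality to anti-saccade accuracy, memory-saccade variability and effort, so Pearson suits links from LRTC to those outcomes.
- That the primary results or the sample size are undermined. The condition regressions, the t-tests and the power in 9.2 concern mean differences and are untouched.

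The wording should be settled before unblinding.

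**What to change.** In 9.4.2, for every correlation that starts from fEI or branching ratio:

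- use the change in distance from 1.0, that is |fEI - 1| or |branching ratio - 1|, taken post minus pre and active minus sham;
- run it separately for cTBS and iTBS, and say so;
- keep the raw signed change for the check that cTBS lowers and iTBS raises E/I, and report its Pearson r descriptively.

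Leave Pearson in place for links from LRTC to behaviour and effort.

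The cost is a sentence or two and no new data. The price is that measurement error biases absolute distance upward near 1.0, and the sham difference does not fully remove this. The gain shrinks, and can vanish, if all baselines sit at 1.0 and fEI is noisy. Reporting the raw-change correlation beside the distance one lets the reader see whether the choice mattered.
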